 - c. Non-measurable (bone) disease: The appearance of two or more new areas of uptake on bone scan (or NaF PET/CT) consistent with metastatic disease compared to previous imaging during castration therapy. The increased uptake of pre-existing lesions on bone scan will not be taken to constitute progression, and ambiguous results must be confirmed by other imaging modalities (e.g. X-ray, CT or MRI).
6. Prior treatment with abiraterone or enzalutamide is permitted, but patients must have been off prior corticosteroid treatment for at least 28 days.
 7. Life expectancy of at least 6 months
 8. Patients must have an ECOG performance status of 0, 1, or 2.
 9. Adequate hematologic, renal and liver function as evidenced by the following within 6 weeks of day 1:

WBC	$\geq 2000 / \text{mm}^3$
ANC	$\geq 1000 / \text{mm}^3$
HgB	$\geq 9.0 \text{ gm/dL}$
Platelets	$\geq 100,000 / \text{mm}^3$
Creatinine	$\leq 2.0 \text{ mg/dL}$
AST, ALT	$\leq 2.5 \times$ institutional upper limit of normal
 10. No known history of HIV 1 and 2, HTLV-1, or active Hepatitis B or Hepatitis C
 11. Patients must be at least 4 weeks from any prior treatments and have recovered (to $<$ Grade 2) from acute toxicity attributed to this prior treatment, unless considered chronic
 12. Patients must be willing and able (in the opinion of the treating physician) to undergo two research biopsies for the investigational component of this trial. See section 6.A for more details.
 13. Patients must be willing to undergo two leukapheresis procedures for the investigational component of this trial
 14. Patients must be willing to undergo FLT PET/CT or NaF PET/CT scans for the investigational component of this trial and have no known allergies to FLT or NaF. See section 9 for more details.
 15. For those patients who are sexually active, they must be willing to use barrier contraceptive methods during the period of treatment on this trial (and for four weeks after the last DNA immunization treatment for patients in Arm 1)
 16. Patients must be informed of the experimental nature of the study and its potential risks, and must sign an IRB-approved written informed consent form indicating such an understanding

B. Exclusion Criteria

1. Small cell or other variant (non-adenocarcinoma) prostate cancer histology, unless there is evidence that the tumor expresses PAP

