Patients will come off study at the time of radiographic (CT and/or bone scintigraphy) disease progression, with progression being defined only AFTER the first 3-month staging evaluation, at the time of undue toxicity (as defined below), or at the discretion of the patient and treating physician that continuing treatment is not in the best interest of the patient and/or that other standard therapies for prostate cancer are warranted due to symptomatic progression. Patients should be discouraged from discontinuing protocol treatment for PSA rise only. NaF and FLT PET/CT scans will be investigational and will not be used for making individual subject treatment decisions with respect to progression necessitating continuing or discontinuing protocol treatment. However, findings on NaF or FLT PET/CT that might pose medical risk to individual subjects will be communicated to the treating physician such that dedicated clinical imaging/intervention could be pursued, if necessary. Such findings on NaF or FLT PET/CT, by themselves, will not be used to define disease progression necessarily requiring patients to come off trial. Patients who, in the discretion of the treating physician, appear to be benefiting (e.g. declining serum PSA and/or

improvement in symptoms despite new radiographic lesions), may continue in protocol treatment/observation after discussion with the PI and study sponsor. Patients will continue to have blood drawn for immune studies, as per study calendar, up to one year after screening, even if off study prior to that time. Patients who undergo an initial research biopsy and/or NaF/FLT PET scan should also undergo the subsequent scans, as long as they are willing, even if they are off study prior to Month 3. In particular, evaluations performed at 6-month time point should be performed even if off-study prior to that time, if feasible. All subjects who have not come off study earlier for these reasons will come off study at the end of one year.

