For patients specifically treated in Arms 3 or 4, the following management rules will apply: If a patient develops Grade 3 toxicity with an attribution of at least possibly related to pembrolizumab and unlikely related (or unrelated) to pTVG-HP vaccine, the pembrolizumab treatment will be held until the toxicity resolves to Grade 1 or less, with the vaccine schedule continuing as per protocol. If a patient develops a second Grade 3 event (or any Grade 4 event) believed to be at least possibly due to pembrolizumab, but unlikely related (or unrelated) to pTVG-HP vaccine, no further pembrolizumab treatments will be given. The patient will continue with pTVG-HP administration only as per protocol. However, if a patient develops a Grade 3 toxicity with an attribution of at least possibly related to pTVG-HP vaccine, both pTVG-HP and pembrolizumab treatment will be

held until the toxicity resolves to Grade 1 or less. If a patient develops a second Grade 3 event (or any Grade 4 event) believed at least possibly related to pTVG-HP vaccine, no further treatments will be given. The patient will remain on study, however, with collection of radiographic and laboratory data as per protocol. The rationale for these modifications is that patients could continue to benefit in terms of anti-tumor response and this could in fact be related to the development of other autoimmune toxicities, and patients who have toxicity from pembrolizumab could still potentially benefit from continued pTVG-HP vaccination.

Specific symptoms and potential adverse events that have been identified in previous trials with pembrolizumab are described below. Management for these specific conditions will be conducted as described, consistent with what has been previously recommended in the FDA prescribing information “package insert”:

Infusion-related reactions:

Treatment with pembrolizumab will be permanently discontinued for grade 3 or 4 infusion-related reaction.

Constitutional symptoms:

Mild, low-grade fevers and chills, and local skin site reactions, are expected events following immunization and/or treatment with GM-CSF. Grade 1 events will not be treated with anti-inflammatory agents unless they persist 48 hours after an immunization. Constitutional inflammatory events > grade 1, or persisting beyond 48 hours after immunization, will be managed with ibuprofen, if needed, up to 600 mg three times daily.

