- G. Immunization #3 - Day 29 (14 +/- 3 days after day 15 visit)
1. Subjects will receive pTVG-HP DNA immunizations intradermally on the deltoid area of the lateral arm (preferentially left arm) with 0.25 mL administered at each of two adjacent sites.
 2. Following vaccinations, the subjects will be observed for 60 minutes for unanticipated adverse events.
- H. Immunization #4 - Day 43 (14 +/- 3 days after day 29 visit)
1. Physical examination, symptoms assessment, and ECOG performance score
 2. Blood draw for CBC, differential and platelets, chemistry panel, PSA and PAP
 3. 10 ml peripheral blood (red-top tubes) for sera to evaluate antibody responses, and 100 ml peripheral blood (green-top heparinized tubes) for T-cell response evaluation and CTC analysis
 4. Subjects will receive pTVG-HP DNA immunizations intradermally on the deltoid area of the lateral arm (preferentially left arm) with 0.25 mL administered at each of two adjacent sites.
 5. Following vaccinations, the subjects will be observed for 60 minutes for unanticipated adverse events.

- I. ARM 1 SUBJECTS ONLY: Anti-PD-1 #3 (Day 43, 1-3 hours after day 43 immunization)
1. Pembrolizumab 2 mg/kg administered intravenously over 30 minutes
 2. Subjects will be observed for additional 30 minutes for unanticipated adverse events. Vital signs (temperature, heart rate and blood pressure) will be assessed and recorded by the staff prior to, and at the end of, the treatment period.
- J. Immunization #5 - Day 57 (14 +/- 3 days after day 43 visit)
1. Subjects will receive pTVG-HP DNA immunizations intradermally on the deltoid area of the lateral arm (preferentially left arm) with 0.25 mL administered at each of two adjacent sites.
 2. Following vaccinations, the subjects will be observed for 60 minutes for unanticipated adverse events.
- K. ARM 1 SUBJECTS ONLY: Anti-PD-1 #4 – Day 64 (7 +/- 3 days after day 57 visit)
1. Physical examination, symptoms assessment, and ECOG performance score
 2. Blood draw for CBC, differential and platelets, chemistry panel, PSA and PAP
 3. Pembrolizumab 2 mg/kg administered intravenously over 30 minutes
 4. Subjects will be observed for an additional 30 minutes for unanticipated adverse events. Vital signs (temperature, heart rate and blood pressure) will be assessed and recorded by the staff prior to, and at the end of, the treatment period.
- L. Immunization #6 - Day 71 (14 +/- 3 days after day 57 visit)

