8. Tissue biopsy – metastatic site – to take place within 2 weeks prior to day 1 (minimum of 6 patients per cohort)

W. Immunization #1 (Day 1)

1. Physical examination, symptoms assessment, and ECOG performance score
2. Blood draw for CBC, differential and platelets, chemistry panel, PSA and PAP
3. Subjects will receive pTVG-HP DNA immunizations intradermally on the deltoid area of the lateral arm (preferentially left arm) with 0.25 mL administered at each of two adjacent sites.
3. Following vaccinations, the subjects will be observed for 60 minutes for unanticipated adverse events.
4. Pembrolizumab 2 mg/kg, maximum 200 mg dose, administered intravenously over 30 minutes
5. Subjects will be observed for additional 30 minutes for unanticipated adverse events.

- X. Immunization #2 - Week 3 (21 +/- 3 days after Day 1 visit)
Immunization #4 - Week 9 (21 +/- 3 days after Week 6 visit)
Immunization #6 - Week 15 (21 +/- 3 days after Week 12 visit)
Immunization #8 - Week 21 (21 +/- 3 days after Week 18 visit)
Immunization #10 - Week 27 (21 +/- 3 days after Week 24 visit)
Immunization #12 - Week 33 (21 +/- 3 days after Week 30 visit)
Immunization #14 - Week 39 (21 +/- 3 days after Week 36 visit)
Immunization #16 - Week 45 (21 +/- 3 days after Week 42 visit)

1. Symptoms assessment
2. Blood draw for CBC, differential and platelets, and chemistry panel (can be performed +/- 3 days of this visit).
3. Blood draw for PSA and PAP (can be performed +/- 3 days of this visit)
4. Subjects will receive pTVG-HP DNA immunizations intradermally on the deltoid area of the lateral arm (preferentially left arm) with 0.25 mL administered at each of two adjacent sites.
5. Following vaccinations, the subjects will be observed for 60 minutes for unanticipated adverse events.
6. Pembrolizumab 2 mg/kg, maximum 200 mg dose, administered intravenously over 30 minutes
7. Subjects will be observed for additional 30 minutes for unanticipated adverse events.

- Y. Immunization #3 – Week 6 (21 +/- 3 days after Week 3 visit)

8. Physical examination, symptoms assessment, and ECOG performance score
9. Blood draw for CBC, differential and platelets, chemistry panel, PSA and PAP
10. 10 ml peripheral blood (red-top tubes) for sera to evaluate antibody responses, and 100 ml peripheral blood (green-top heparinized tubes) for T-cell response evaluation and CTC analysis (can be performed +/- 7 days of this visit)

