Immunization #22 - Week 42 (14 +/- 3 days after Week 40 visit)

Immunization #24 - Week 46 (14 +/- 3 days after Week 44 visit)

1. Symptoms assessment
2. Subjects will receive pTVG-HP DNA immunizations intradermally on the deltoid area of the lateral arm (preferentially left arm) with 0.25 mL administered at each of two adjacent sites.
3. Following vaccinations, the subject will be observed for 60 minutes for unanticipated adverse events.

KK. Immunization #4 – Week 6 (14 +/- 3 days after Week 4 visit)

1. Symptoms assessment
2. 10 ml peripheral blood (red-top tubes) for sera to evaluate antibody responses, and 100 ml peripheral blood (green-top heparinized tubes) for T-cell response evaluation and CTC analysis (can be performed +/- 7 days of this visit)
3. Subjects will receive pTVG-HP DNA immunizations intradermally on the deltoid area of the lateral arm (preferentially left arm) with 0.25 mL administered at each of two adjacent sites.
4. Following vaccinations, the subject will be observed for 60 minutes for unanticipated adverse events.
5. NaF PET/CT scan +/- 7 days from this visit (only if baseline NaF PET/CT obtained)

LL. Immunization #3 - Week 4 (14 +/- 3 days after Week 2 visit)
Immunization #5 - Week 8 (14 +/- 3 days after Week 6 visit)
Immunization #9 - Week 16 (14 +/- 3 days after Week 14 visit)
Immunization #11 - Week 20 (14 +/- 3 days after Week 18 visit)
Immunization #15 - Week 28 (14 +/- 3 days after Week 26 visit)
Immunization #17 - Week 32 (14 +/- 3 days after Week 30 visit)
Immunization #21 - Week 40 (14 +/- 3 days after Week 38 visit)
Immunization #23 - Week 44 (14 +/- 3 days after Week 42 visit)

1. Physical examination, symptoms assessment, and ECOG performance score.
2. Blood draw for CBC, chemistry panel, serum PSA and PAP (can be performed up to 3 days prior to this visit)
3. Subjects will receive pTVG-HP DNA immunizations intradermally on the deltoid area of the lateral arm (preferentially left arm) with 0.25 mL administered at each of two adjacent sites.
4. Following vaccinations, the subject will be observed for 60 minutes for unanticipated adverse events.
5. Pembrolizumab 2 mg/kg, maximum dose 200 mg, administered intravenously over 30 minutes
6. Subjects will be observed for additional 30 minutes for unanticipated adverse events.

MM. Immunization #7 - Week 12 (14 +/- 3 days after Week 10 visit)
Immunization #19 - Week 36 (14 +/- 3 days after Week 34 visit)

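### Inclusion item 15 limits the four-week contraception period after the last DNA dose to Arm 1, although Arms 3 and 4 also end on a DNA dose

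*Combined protocol and SAP*

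**What the plan says.** Item 15 of the inclusion criteria (protocol Section 5.A) has two parts. The first applies to everyone: "For those patients who are sexually active, they must be willing to use barrier contraceptive methods during the period of treatment on this trial". The second, in brackets, adds a follow-on period "for four weeks after the last DNA immunization treatment for patients in Arm 1". Arms 2, 3 and 4 are not mentioned in it.

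Section 9 gives the last DNA dose in each arm. For Arms 1 and 2 it is "Immunization #6 - Day 71 (14 +/- 3 days after day 57 visit" (9.L). For Arm 3 it is "Immunization #16 - Week 45 (21 +/- 3 days after Week 42 visit" (9.X), with pembrolizumab at the same visit. For Arm 4 it is "Immunization #24 - Week 46 (14 +/- 3 days after Week 44 visit" (9.JJ), a vaccine-only visit.

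Section 8 has a rule specific to Arms 3 and 4. When pembrolizumab is stopped for toxicity considered unlikely related or unrelated to the vaccine: "The patient will continue with pTVG-HP administration only as per protocol".

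The only other contraception text is in Section 14 A.8, among the risks of the FLT and NaF PET scans. It asks patients to avoid conception while they are participating in the study. Section 14 A.1, which covers the risks of the DNA vaccine, gives no contraception period.

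**The concern.** The restriction to Arm 1 makes sense for a two-arm trial. Arm 1 ends on a DNA dose, so it needs a stated period afterwards. A completed Arm 2 course continues on pembrolizumab well beyond four weeks after the last DNA dose, so the treatment period already supplies the cover.

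Arms 3 and 4 came later and resemble Arm 1 in this respect: the last visit with treatment includes a DNA dose. They use the same 100 µg plasmid dose and allow up to 16 and 24 doses, against 6 in Arm 1. The protocol offers no reason to apply the precaution to the arm with fewest doses and leave it off the arms with most. Exclusion item 17 was worded with Arms 3 and 4 in mind, so Section 5 was revised for them, and item 15 looks overlooked rather than deliberate.

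A precaution that the sponsor chose to set after the last DNA dose would not, if staff follow item 15 as written, clearly reach the two extended-treatment arms.

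**Working it through.** The plan's only figure here is the four-week period, 4 × 7 = 28 days. The check is a comparison of schedules.

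**Inputs**
- Arm 1: last pembrolizumab Day 64 (9.K); last DNA Day 71 (9.L).
- Arm 2: last DNA Day 71; pembrolizumab on Days 85, 106, 127 and 148 (9.M to 9.P).
- Arm 3: DNA and pembrolizumab together every 3 weeks, last at week 45 (9.X); final visit week 48 (9.DD).
- Arm 4: DNA every 2 weeks, last at week 46 (9.JJ); last pembrolizumab week 44 (9.LL); final visit week 48 (9.OO). The Arm 4 calendar table did not survive text extraction cleanly, so Section 9 was used.
- These agree with the dose maxima in Section 6: Arm 3, 45/3 + 1 = 16 of each; Arm 4, 46/2 + 1 = 24 DNA and 44/4 + 1 = 12 pembrolizumab.

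**Step 1. Which agent comes last** (last pembrolizumab minus last DNA)
- Arm 1: 64 − 71 = −7 days. Ends on DNA.
- Arm 2: 148 − 71 = +77 days. Ends on pembrolizumab.
- Arm 3: 45 − 45 = 0. Both at one visit.
- Arm 4: (44 − 46) × 7 = −14 days. Ends on DNA.

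**Step 2. Days of contraception after the last DNA dose under item 15, for completers of Arms 3 and 4**

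| Reading of the treatment period | Arm 3 | Arm 4 |
|---|---|---|
| Ends at the last dose | 0 (28 short) | 0 (28 short) |
| Runs to the week 48 visit | (48 − 45) × 7 = 21 (7 short) | (48 − 46) × 7 = 14 (14 short) |

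The ±3-day window on the week 48 visit gives 18 to 24 days in Arm 3 and 11 to 17 in Arm 4, still under 28. The protocol does not define the term. Section 8 counts 12 weeks of treatment for Arm 1 and 24 for Arm 2, which run past the last doses on Days 71 and 148, and Arm 4's week 48 visit is labelled as the end of treatment. Arm 3's is labelled as the end of study. Neither reading can be excluded, and both fall short.

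**Step 3. Does Section 14 A.8 close the gap?** Its stated reason is the tracers. Arm 4 has no FLT scan, and NaF scans are limited to 10 evaluable patients across Arms 3 and 4 (Section 9), so many of these patients receive no tracer. If A.8 is nonetheless taken as general, the answer depends on when participation ends:
- At week 48: 21 and 14 days, as above.
- At one year under Section 6.B ("All subjects who have not come off study earlier for these reasons will come off study at the end of one year"), assuming the year runs from Day 1: (52 − 45) × 7 = 49 days in Arm 3 and (52 − 46) × 7 = 42 in Arm 4, both above 28. The starting point of the year is not stated; an earlier one shortens both.
- If the 28-day visit for patients leaving before week 48, or the two years of annual telephone contact, counts as participation, the four weeks could also be covered.

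The text does not choose among these.

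**Step 4. Arm 2 patients who stop early.** Day 85 is 85 − 71 = 14 days after the last DNA dose (11 to 17 with the window). Day 106 is 106 − 71 = 35 days after it (11 + 18 = 29 to 17 + 24 = 41). So four weeks are already covered for anyone treated on Day 106, and only those who stop before then lack them.

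**Step 5. With the restriction removed.** Arm 1: 71 + 28 = Day 99, unchanged. Arm 3: 45 + 4 = week 49. Arm 4: 46 + 4 = week 50.

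**The case against.** Nobody can point to a sentence that gives Arms 3 and 4 a four-week period after the last DNA dose. The case on the other side is about reach and weight, and much of it stands.

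- **Arm 2.** A reader might infer a continuing gap for Arm 2 patients who stop in the vaccine phase. Section 6.A closes Arms 1 and 2 to accrual once Arm 3 opens, and Section 2.F reports 11 patients already in Arm 3 by January 2018. The Arm 2 gap is real on paper but largely moot.
- **DNA alone after toxicity.** It is tempting to say that every Arm 3 or 4 patient who stops pembrolizumab for toxicity goes on with DNA. Section 8 allows this only when the event is unlikely related or unrelated to the vaccine. A second Grade 3 event or any Grade 4 event at least possibly related to the vaccine ends both agents.
- **Patients left without protection.** That would be a stronger claim than the documents allow. The treatment period and the study participation period are both undefined, some readings of A.8 exceed four weeks, and the consent form was not available for this review. What can be shown is that item 15 gives the wrong coverage, not that patients receive no instruction.
- **Hazard.** Patients must be castrate, with testosterone below 50 ng/dL; Section 14 A.1 itself rates transfer to offspring as unlikely; and the protocol gives no rationale for choosing four weeks. No quantified harm follows from losing one or two of them.

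What survives is the error in item 15 for Arms 3 and 4. It is a stated rule with the wrong scope rather than a missing detail, and site staff should not have to infer a vaccine precaution from the PET section.

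**Conclusion.** The point holds as a minor safety-wording correction, worth making because the text is wrong as it stands. Item 15 confines the four-week period after DNA to Arm 1, while Arms 3 and 4 also end on a DNA dose. For completers the shortfall against 28 days is 28 days in both arms if treatment ends at the last dose, or 7 days (Arm 3) and 14 days (Arm 4) if it runs to week 48.

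The number of patients concerned is unknown. It is the sexually active share of the 40 evaluable patients planned for the two arms (20 + 20), and the documents do not give that share. Because some Arm 3 patients were enrolled before Arm 4 was added, a change to an eligibility criterion would reach fewer than 40 new entrants.

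Confidence is high about item 15's wording and the dosing schedule. It does not extend to what patients are actually told, which depends on the unseen consent form. Endpoints, sample size, power, analysis populations and visits are unaffected.

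**What to change.** In Section 5.A, item 15, delete the closing words that restrict the follow-on period to Arm 1, so that barrier contraception continues through treatment and for four weeks after the last DNA immunization in every arm. This also covers patients who stop early, including any in Arm 2. Add one matching sentence to Section 14 A.1, where the vaccine's risks are described, and to the consent form if it does not already say this. Tell patients already on treatment directly, since an eligibility criterion will not reach them.

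The cost is small. Completers continue contraception about one week (Arm 3, to week 49) or two weeks (Arm 4, to week 50) beyond the week 48 visit, and patients who stop early continue for four weeks from their last DNA dose. Nothing changes for Arm 1 or for Arm 2 patients treated on Day 106, and no visits, data or analyses are added.
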